### 8.6.2 Intensity Modulated Radiation Therapy (IMRT)

IMRT is allowed in this study. The use of IMRT in this study is at the discretion of the treating physician. However, IMRT should be considered only when target coverage, OAR dose limits, or dose spillage are not achievable with 3D conformal planning. In addition, IMRT plans should follow the same planning principles as discussed above for 3D conformal planning. The number of segments (control points) and the area of each segment should be optimized to ensure deliverability and avoid complex beam fluences. Ideally, the number of segments should be minimized (2-3 segments per beam should be adequate), and the area of each segment should be maximized (the aperture of one segment from each beam should correspond to the projection of the PTV along a beam's eye view).

### 8.6.3 Dose Calculations

For purposes of dose planning and calculation of monitor units for actual treatment, this protocol will require tissue density heterogeneity correction.

Successful treatment planning will require accomplishment of all of the following criteria:

**Maximum dose:** The treatment plan should be created such that 100% corresponds to the maximum dose delivered to the patient. This point must exist within the PTV.

**Prescription isodose:** The prescription isodose surface must be  $\geq 60\%$  and  $< 90\%$  of the maximum dose.

**Prescription Isodose Surface Coverage:** The prescription isodose surface will be chosen such that 95% of the target volume (PTV) is conformally covered by the prescription isodose surface (PTV V95%RX = 100%) and 99% of the target volume (PTV) receives a minimum of 90% of the prescription dose (PTV V90%RX > 99%).

### 8.6.4 Normal Tissue Dose Constraints

In accordance with the prior Phase I studies [7, 8], certain normal tissue dose constraints must be respected.

The possibility that SABR-induced fibrosis might cause occlusion of large central airways, thus impeding ventilation distal to the occlusion has been well considered. An adjustment to the fractionation scheme may be made if, in the opinion of the treating radiation oncologist, the following conditions apply: (1) the location of a lung lesion is close enough to a large proximal bronchial airway such that occlusion might occur, and (2) compromised ventilation to the segment(s) of lung potentially affected would cause clinically significant adverse consequences.

The same special condition applies in the setting of a patient whose primary lung disease has not been irradiated previously but is present as a PET-positive site of disease, often in proximity to mediastinal structures which is a dose-limiting concern. These patients will be considered by the PI on a case-by-case basis.

The following table lists the specific organ and dose fractionation constraints on normal tissues.

#### One Fraction

Serial Tissue	Volume	Volume Max (Gy)	Max Point Dose (Gy)**	Endpoint (≥Grade 3)
Spinal Cord and medulla	<0.35 cc <1.2 cc	10 Gy 8 Gy	14 Gy	myelitis
Spinal Cord Subvolume (5-6 mm above and below level treated per Ryu)	<10% of subvolume	10 Gy	14 Gy	myelitis
Cauda Equina	<5 cc	14 Gy	16 Gy	neuritis
Sacral Plexus	<5 cc	14.4 Gy	16 Gy	neuropathy
Esophagus*	<5 cc	11.9 Gy	15.4 Gy	stenosis/fistula
Brachial Plexus	<3 cc	13.6 Gy	16.4 Gy	neuropathy
Heart/Pericardium	<15 cc	16 Gy	22 Gy	pericarditis
Great vessels	<10 cc	31 Gy	37 Gy	aneurysm
Trachea and Large Bronchus*	<4 cc	17.4 Gy	20.2 Gy	stenosis/fistula
Bronchus- smaller airways	<0.5 cc	12.4 Gy	13.3 Gy	stenosis with atelectasis
Rib	<5 cc	28 Gy	33 Gy	Pain or fracture
Skin	<10 cc	25.5 Gy	27.5 Gy	ulceration
Stomach	<5 cc	17.4 Gy	22 Gy	ulceration/fistula
Bile duct			30 Gy	stenosis
Duodenum*	<5 cc <10 cc	11.2 Gy 9 Gy	17 Gy	ulceration
Jejunum/Ileum*	<30 cc	12.5 Gy	22 Gy	enteritis/obstruction
Colon*	<20 cc	18 Gy	29.2 Gy	colitis/fistula
Rectum*	<3.5 cc <20 cc	39 Gy 22 Gy	44.2 Gy	proctitis/fistula
Ureter			35 Gy	stenosis
Bladder wall	<15 cc	12 Gy	25 Gy	cystitis/fistula
Penile bulb	<3 cc	16 Gy		impotence
Femoral Heads	<10 cc	15 Gy		necrosis
Renal hilum/vascular trunk	15 cc	14 Gy		malignant hypertension
Parallel Tissue	Critical Volume (cc)	Critical Volume Dose Max (Gy)		Endpoint (≥Grade 3)

STU042015-076, [name], FormA-ResearchProtocol-V6, Mod\_19, 04-09-20 (1)

CONFIDENTIAL

This material is the property of the [UTSW Simmons Cancer Center](#). Do not disclose or use except as authorized in writing by the study sponsor.

Lung (Right & Left)	1500 cc	7 Gy		Basic Lung Function
Lung (Right & Left)	1000 cc	7.6 Gy	V-8Gy <37%	Pneumonitis
Liver	700 cc	11 Gy		Basic Liver Function
Renal cortex (Right & Left)	200 cc	9.5 Gy		Basic renal function

\*Avoid circumferential irradiation

\*\* “point” defined as 0.035cc or less

### Three Fractions

Serial Tissue	Volume	Volume Max (Gy)	Max Point Dose (Gy)**	Endpoint (≥Grade 3)
Spinal Cord and medulla	<0.35 cc <1.2 cc	15.9 Gy 13 Gy	22.5 Gy	myelitis
Spinal Cord Subvolume (5-6 mm above and below level treated per Ryu)	<10% of subvolume	18 Gy	22.5 Gy	myelitis
Cauda Equina	<5 cc	21.9 Gy	25.5 Gy	neuritis
Sacral Plexus	<5 cc	22.5 Gy	24 Gy	neuropathy
Esophagus*	<5 cc	17.7 Gy	25.2 Gy	stenosis/fistula
Brachial Plexus	<3 cc	22 Gy	26 Gy	neuropathy
Heart/Pericardium	<15 cc	24 Gy	30 Gy	pericarditis
Great vessels	<10 cc	39 Gy	45 Gy	aneurysm
Trachea and Large Bronchus*	<5 cc	25.8 Gy	30 Gy	stenosis/fistula
Bronchus- smaller airways	<0.5 cc	18.9 Gy	23.1 Gy	stenosis with atelectasis
Rib	<5 cc	40 Gy	50 Gy	Pain or fracture
Skin	<10 cc	31 Gy	33 Gy	ulceration
Stomach	<5 cc	22.5 Gy	30 Gy	ulceration/fistula
Bile duct			36 Gy	stenosis
Duodenum*	<5 cc <10 cc	15.6 Gy 12.9 Gy	22.2 Gy	ulceration
Jejunum/Ileum*	<30 cc	17.4 Gy	27 Gy	enteritis/obstruction
Colon*	<20 cc	24 Gy	34.5 Gy	colitis/fistula
Rectum*	<3.5 cc <20 cc	45 Gy 27.5 Gy	49.5 Gy	proctitis/fistula
Ureter			40 Gy	stenosis
Bladder wall	<15 cc	17 Gy	33 Gy	cystitis/fistula
Penile bulb	<3 cc	25 Gy		impotence
Femoral Heads	<10 cc	24 Gy		necrosis
Renal hilum/vascular trunk	15 cc	19.5 Gy		malignant hypertension
Parallel Tissue	Critical Volume (cc)	Critical Volume Dose Max (Gy)		Endpoint (≥Grade 3)
Lung (Right & Left)	1500 cc	10.5 Gy		Basic Lung Function
Lung (Right & Left)	1000 cc	11.4 Gy	V-11Gy<37%	Pneumonitis
Liver	700 cc	17.1 Gy		Basic Liver Function
Renal cortex (Right & Left)	200 cc	15 Gy		Basic renal function

\*Avoid circumferential irradiation

\*\* “point” defined as 0.035cc or less

### Five Fractions

Serial Tissue	Volume	Volume Max (Gy)	Max Point Dose (Gy)**	Endpoint (≥Grade 3)
---------------	--------	-----------------	-----------------------	---------------------

Spinal Cord and medulla	<0.35 cc <1.2 cc	22 Gy 15.6 Gy	28 Gy	myelitis
Spinal Cord Subvolume (5-6 mm above and below level treated per Ryu)	<10% of subvolume	22 Gy	28 Gy	myelitis
Cauda Equina	<5 cc	30 Gy	31.5 Gy	neuritis
Sacral Plexus	<5 cc	30 Gy	32 Gy	neuropathy
Esophagus*	<5 cc	19.5 Gy	35 Gy	stenosis/fistula
Brachial Plexus	<3 cc	27 Gy	32.5 Gy	neuropathy
Heart/Pericardium	<15 cc	32 Gy	38 Gy	pericarditis
Great vessels	<10 cc	47 Gy	53 Gy	aneurysm
Trachea and Large Bronchus*	<5 cc	32 Gy	40 Gy	stenosis/fistula
Bronchus- smaller airways	<0.5 cc	21 Gy	33 Gy	stenosis with atelectasis
Rib	<5 cc	45 Gy	57 Gy	Pain or fracture
Skin	<10 cc	36.5 Gy	38.5 Gy	ulceration
Stomach	<5cc	26.5 Gy	35 Gy	ulceration/fistula
Bile duct			41 Gy	stenosis
Duodenum*	<5 cc <10 cc	18.5 Gy 14.5 Gy	26 Gy	ulceration
Jejunum/Ileum*	<30 cc	20 Gy	32 Gy	enteritis/obstruction
Colon*	<20 cc	28.5 Gy	40 Gy	colitis/fistula
Rectum*	<3.5 cc <20 cc	50 Gy 32.5 Gy	55 Gy	proctitis/fistula
Ureter			45 Gy	stenosis
Bladder wall	<15 cc	20 Gy	38 Gy	cystitis/fistula
Penile Bulb	<3 cc	30 Gy		impotence
Femoral Heads	<10 cc	30 Gy		necrosis
Renal hilum/vascular trunk	15 cc	23 Gy		malignant hypertension
Parallel Tissue	Critical Volume (cc)	Critical Volume Dose Max (Gy)		Endpoint (≥Grade 3)
Lung (Right & Left)	1500 cc	12.5 Gy		Basic Lung Function
Lung (Right & Left)	1000 cc	13.5 Gy	V-13.5Gy<37%	Pneumonitis
Liver	700 cc	21 Gy		Basic Liver Function
Renal cortex (Right & Left)	200 cc	18 Gy		Basic renal function

\*Avoid circumferential irradiation

\*\* “point” defined as 0.035cc or less

Exceeding these dose tolerances by more than 2.5% constitutes a minor protocol violation. Exceeding these dose tolerances by more than 5% constitutes a major protocol violation.

## 8.7 Intracranial Stereotactic Radiosurgery Dose (SRS) for and Technique

Patients with up to 10 brain metastases with the maximal size  $\leq 4$ cm will be treated by SRS in a single fraction. If there are more than 10 intracranial lesions or the size of the largest lesion is  $>4$ cm, such patients will be ineligible.

### 8.7.1 SRS Dose

All supratentorial lesions are treated to the prescribed dose below.

	SRS Dose by lesion diameter		
Diameter (cm)	$\leq 2.0$ cm	$>2.0 - 3.0$ cm	$>3.0 - 4.0$ cm
Dose (Gy)	20-24	18	15

For lesions within the brainstem (pons, medulla, and midbrain), the prescription dose will be 10-13 Gy in a single fraction.

Multiple SRS sessions are allowed, as long as all intracranial lesions are treated within 14 days.

### 8.7.2 SRS Technique, Pre-SRS Image acquisition and target planning with Conformality Index

Protocol SRS will be administered with a linear accelerator (LINAC), Vero® (BrainLab, Feldkirchen, Germany), CyberKnife® (Accuray, Sunnyvale, CA) or Gamma Knife® Perfection (Elektra Instruments, Inc., Atlanta, GA). Fixed-frame stereotactic localization and planning will be used for SRS.

Pre-SRS Image Acquisition: MRI with gadolinium contrast is the recommended imaging method for stereotactic localization. In the case of LINAC, Vero or CyberKnife, MRI with contrast has to be obtained within 14 days of SRS with an acquisition of  $\leq 1.5$  mm slice thickness. The stereotactic target is the contrast-enhancing tumor as defined on MRI with contrast.

In patients who cannot tolerate the contrast, other MR sequences may be utilized without the contrast, as long as the target lesion can be clearly demarcated for treatment and follow up.

Conformality Index (CI) is derived from dividing the volume encompassed by the prescription isodose line by the target volume.

$$CI = \text{Rx Isodose Vol} / (\text{Target Vol})$$

The target lesion in the SRS planning MRI will be contoured, and its volume will be calculated. Planning should achieve a conformity index specified below.

Size of Target	Prescription Isodose	Conformality Index
$\leq 1$ cm	35-100%	$\leq 2$
1-2cm		$\leq 2$

2-3cm		≤ 1.5
3-4cm		≤ 1.25

At least 95% of the target volume must receive the prescription dose; the plan should be adjusted to achieve such coverage by the isodose line between 40-100%. No part of the target should receive less than 90% of the prescription dose.

### 8.7.3 Normal Tissue Dose Constraints

The following table lists maximum dose limits, in one fraction, to a point or volume within several critical structures of the cranium. These are absolute limits, and treatment delivery that exceeds these limits will constitute a major protocol violation.

Critical Structure and margin	Volume	Volume Max (Gy)	Max Point Dose (Gy)*	Endpoint (≥Grade 3)
Optic Pathway	<0.2 cc	8 Gy	10 Gy	neuritis
Brainstem (not medulla)	<0.5 cc	10 Gy	15 Gy	cranial neuropathy
Spinal Cord and medulla	<0.35cc <1.2 cc	10 Gy 8 Gy	14 Gy	myelitis

\* “point” defined as 0.035cc or less

Patients with lesions within or near the above structures and the dose constraints cannot be satisfied, will be deemed ineligible.

## 8.8 Radiation Therapy Quality Assurance

The radiation oncologist will perform an RT Quality Assurance Review after complete data for the first half of cases (18) enrolled at the University of Texas Southwestern Medical Center. They will perform the final review after complete data for the subsequent 19 cases at the University of Texas Southwestern Medical Center are completed. These cases will be reviewed within 3 months after this study has reached the target accrual or as soon as complete data for all cases enrolled has been received, whichever occurs first.

## 9.0 STATISTICAL CONSIDERATIONS

### 9.1 Study Design/Study Endpoints

This is an, open-label, two-cohort protocol designed to evaluate the activity of targeted therapy and SABR in *ALK* positive lung adenocarcinoma.

Cohort A will evaluate the combination in *ALK*-inhibitor naïve patients.

Cohort B will evaluate the combination in patients who have received treatment with one prior *ALK* inhibitor.

Ceritinib will be administered to the patient until disease progression by RECIST 1.1, unacceptable toxicity, withdrawal of consent, or discontinuation of the trial for any other reason including death.

The primary focus of this protocol is identifying response in *ALK*+ lung cancer patients. Patients with IHC positive or FISH probe positive tumors will be treated. Evidence of *ALK* gene rearrangement will also be considered eligible for the trial.

**Study Design:**

**Purpose:** of this prospective, single-center, two cohort, non-randomized trial is to evaluate the impact of the combination of ceritinib and stereotactic radiation delivered to patients with *ALK*-rearranged adenocarcinoma. The enhanced efficacy of this combination is to be evaluated specifically with regards to prolongation of clinical benefit of ceritinib. We will also evaluate the safety of this combination of targeted therapy and radiation.

For *ALK*-rearranged patients started on ceritinib and treated with SABR to persisting lesions:  
 -PFS compared to published historical results with ceritinib alone PFS=7 month for prior crizotinib treated and 10 month for no previous crizotinib therapy (Shaw et al, NEJM 2014).  
 PFS will be defined as Time to Subsequent Systemic Therapy.

As secondary objectives, we will also report overall survival and time to 2nd and 3rd SABR for each cohort.

	Objective	Endpoint
Primary:	Cohort A: Superiority of ceritinib + SABR median PFS compared to historical control of 10 months (expected to be 20 months)  Cohort B: Superiority of ceritinib + SABR median PFS compared to historical control of 7 months	Cohort A Median PFS defined as time from initiation of ceritinib until disease progression by RECIST 1.1, unacceptable toxicity, withdrawal of consent, or discontinuation of the trial for any other reason including death.  Cohort B: Median PFS defined as time from initiation of ceritinib until disease progression by RECIST 1.1, unacceptable toxicity, withdrawal of consent, or discontinuation of the trial for any other reason including death.
Secondary:	Report Overall survival  Report Time to 2 nd SABR  Report Time to 3 rd SABR  Report proportion of patients CR/PR/stable disease at 6 and 12 months	Overall survival  Time from start of systemic therapy to first day of second course of SABR  Time from start of therapy to first day of third course of SABR  Number of patients with CR/PR/stable disease for 6 and 12 months after initiation
Safety:	Demonstrate safety of ceritinib followed by SABR	Describe toxicity and adverse events (CTCAE v.4) compared to historical controls.

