### 2.2.1 Treatment phase and duration of treatment

Patients eligible for treatment will receive 450 mg daily of ceritinib as part of a 28 day cycle. The first dose of each cycle will be administered after evaluation at the study center. Patients will remain on study and take ceritinib until there is evidence of disease progression by RECIST 1.1, unacceptable toxicity, withdrawal of consent, or discontinuation of the trial for any other reason. In case of oligoprogression amenable to repeat courses of SABR, the treating oncologist may resume ceritinib if it is indicated per standard clinical practice. Patients must continue to be followed for safety and efficacy assessments as per the schedule of assessments.

After 2 treatment cycles, lesions will be assessed by treating physician per RECIST 1.1. Persisting lesions will be treated with a course of SABR as feasible following at least 10 weeks of ceritinib treatment. Ceritinib will be held 3 days before the start of radiation. Patients will resume ceritinib 3 days

after completion of the SABR. Regular surveillance will follow and any new or enlarging lesions that develop will be assessed for repeat SABR.

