### *Cohort A (no prior ALK-inhibitor):*

A sample size of 18 patients achieves 80% power to detect the difference between the null hypothesis of median PFS of 10 months and the alternative hypothesis of median PFS of 20 months at two-sided significance level of 0.1. We assume the patient accrual period of 36 months and the follow-up period of 12 months. The assumption that patients are randomized until the end of accrual. The sample size was estimated using SWOG ([https://www.swogstat.org/stat/public/one\\_survival.htm](https://www.swogstat.org/stat/public/one_survival.htm)) sample size calculator.

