### **9.7 Statistical methods and data analysis**

### **9.8 Analysis sets**

#### **9.8.1 Full Analysis Set**

The Full Analysis Set (FAS) comprises all enrolled patients.

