### **9.9 Patient demographics/other baseline characteristics**

Demographic, disease characteristics and other baseline data will be summarized descriptively for the FAS.

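### Section 9.1 states the benchmark PFS comparison for SABR-treated patients but times PFS from ceritinib start, at least 10 weeks earlier, and no analysis set is assigned to PFS

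*Combined protocol and SAP*

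**What the plan says.** Section 9.1 (Study Design) introduces the comparison for "patients started on ceritinib and treated with SABR to persisting lesions". It sets their PFS against the figures published for ceritinib alone: 7 months after prior crizotinib and 10 months without it. The endpoint table in the same section starts the clock earlier, for both cohorts: "Median PFS defined as time from initiation of ceritinib until disease progression by RECIST 1.1". Toxicity, consent withdrawal, any other discontinuation and death also count as events. Section 9.1 gives a second definition of PFS as well, time to subsequent systemic therapy.

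On timing, section 2.2.1 says: "Persisting lesions will be treated with a course of SABR as feasible following at least 10 weeks of ceritinib treatment". Sections 1.4 and 8.3 also give 10 weeks, and section 1.4 adds that there is no fixed window.

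On analysis sets, section 9.8.1 says: "The Full Analysis Set (FAS) comprises all enrolled patients". The only analysis tied to that set is in section 9.9: "Demographic, disease characteristics and other baseline data will be summarized descriptively for the FAS". The Safety Set (at least one ceritinib dose, section 9.8.2) is assigned to exposure and safety in section 9.10. Section 9.3 names Kaplan-Meier estimation for PFS, but no analysis set and no test against the benchmark.

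**The concern.** Receiving SABR is a post-baseline event. If only SABR recipients are counted, but from ceritinib start, most have to get through about 10 weeks without failing before they can enter the analysis. Patients who die, stop for toxicity, withdraw or need new systemic therapy before SABR drop out of the comparison. So do patients whose residual disease cannot all be irradiated, because section 1.3.3 says all gross tumour should be treated for a patient to continue. The benchmark is for ceritinib alone, so receipt of SABR was not a condition of being counted in it.

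This is immortal-time selection. It lengthens apparent PFS whether or not SABR works, in the direction of the superiority claim, in both cohorts. With 18 and 15 patients and no concurrent control, nothing in the data would reveal it.

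**Working it through.** **Inputs (section 9.2).** Cohort A: "A sample size of 18 patients achieves 80% power to detect the difference between the null hypothesis of median PFS of 10 months", against "the alternative hypothesis of median PFS of 20 months", "at two-sided significance level of 0.1". Cohort B: 15 patients, 7 against 14 months, same power and level. Both: 36 months' accrual plus 12 months' follow-up. Two-sided 0.1 is 5% in the direction of benefit, critical value 1.645.

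**Reproducing the plan's sample size.** Assume exponential PFS with rate λ = ln 2 / median and uniform accrual. The event probability is p = 1 − [exp(−12λ) − exp(−48λ)] / (36λ).
- Expected events, null / alternative: A 15.12 / 11.22; B 13.75 / 11.14.
- Log-hazard test: power = Φ{√d1 × (ln 2 − 1.645/√d0)}, with d0 and d1 the expected events under null and alternative.
- A: √11.22 × (0.693 − 1.645/√15.12) = 0.905, power 81.7%. B: √11.14 × (0.693 − 1.645/√13.75) = 0.833, power 79.8%.
- Solving for 80% gives 18 and 16 patients; a cube-root version gives 17 and 15. The stated 18 and 15 are reproduced closely enough to use this model.

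**Early events under the null.** 10 weeks = 70/30.4375 = 2.30 months. The share with an event by then is 1 − 2^(−2.30/median).
- A: 1 − 2^(−0.230) = 14.7%. B: 1 − 2^(−0.329) = 20.4%.
- If all of them are left out, the apparent median with inactive SABR is 10 + 2.30 = 12.3 months (A) and 7 + 2.30 = 9.3 months (B).

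**False-positive rate.** If a fraction q of the early-event patients is left out, early events make up p(1 − q)/(1 − pq) of those counted, where p is now 14.7% or 20.4%. At q = 0.5 that is 0.0737/0.9263 = 8.0% (A) and 0.1018/0.8982 = 11.3% (B). With 200,000 simulated null trials per row and 18 and 15 patients counted, the range in each cell runs from the cube-root test to the one-sample log-rank test with variance (O+E)/2:

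| Early-event patients left out | Cohort A | Cohort B |
|---|---|---|
| none | 4.7–5.2% | 4.5–5.0% |
| 25% | 6.1–6.8% | 6.2–6.9% |
| 50% | 8.2–9.0% | 8.7–9.6% |
| 75% | 10.9–11.9% | 12.4–13.5% |
| all | 14.7–15.9% | 17.5–19.0% |

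**Sensitivity of the last row.**
- *Smaller counted set.* If those left out are not made up, about 18 × 0.853 = 15 and 15 × 0.796 = 12 patients remain. The log-rank rates are then about 14% (A) and 16% (B).
- *Choice of test.* With variance E, the log-rank test starts at about 3.5% and reaches about 12% (A) and 14% (B) with 18 and 15 counted.
- *Later SABR.* SABR at week 12 gives 17.8–19.2% (A) and 22.0–23.7% (B).
- *Complete responders.* Patients with nothing left to irradiate at week 10 would also fall outside a SABR-only set, and they tend to have long PFS. If they are 10% of patients, weighted 3:1 to long PFS, the rates are about 11% (A) and 12% (B). Both figures are assumptions; the documents give no rate.

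**The case against.** The strongest reply is that the phrase in section 9.1 describes the regimen and does not define an analysis set. Much of the protocol supports this:
- The Study Summary bases the comparison on patients treated on the protocol, and section 4.1 says treatment means ceritinib.
- Section 2.0 gives the primary endpoint for the study cohort, and cohorts are fixed at entry by prior ALK-inhibitor exposure (sections 2.0 and 3.2), not by SABR.
- The endpoint table in section 9.1 carries no SABR restriction.
- Section 2.3 ends the study when all 33 patients (18 + 15) have had an endpoint, and section 5.2.3.3 bars replacement once drug has been taken. A SABR-only set would fall short of the planned 18 and 15.

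All of that stands, so section 9.1 is not the only statement of who is compared. But none of these places assigns an analysis set to PFS, and the contrary wording sits in the statistical section, beside the benchmark figures.

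A reader might also infer that every counted patient is guaranteed 10 event-free weeks, and that an inactive SABR therefore passes three times as often as it should. The documents do not support that without conditions. Section 1.3.3 lets patients whose lesions progressed on ceritinib alone go on to SABR. The first scan comes after two cycles, about 8 weeks (sections 2.2.1 and 5.3.1). Sections 1.3.3 and 6.1.6 count the first progression as the PFS event even if ceritinib resumes. Such patients enter a SABR-treated set with an early event already recorded. The guarantee is complete only under the time-to-subsequent-systemic-therapy definition.

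**Conclusion.** The plan conflicts with itself on who is in the primary comparison, and one of its two readings is biased toward success. The bias is not certain: if all ceritinib-treated patients are analysed there is none.

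Under the SABR-treated reading the size depends on how many early-event patients are lost. The false-positive rate is about 8–10% if half are lost. It reaches an upper end of about 14–16% in Cohort A and 16–19% in Cohort B if all are lost, against a nominal 5%. The lower figures in the upper-end ranges fit the plan's no-replacement rule; the higher ones suppose 18 and 15 SABR-treated patients.

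These figures rest on exponential PFS, SABR at exactly week 10 and an assumed one-sample test. Later SABR would raise them and week-10 complete responders would lower them. The direction of the loss of early failures does not depend on these assumptions. Because it concerns the primary endpoint of both cohorts, it should be settled before analysis.

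**What to change.** In sections 9.1 and 9.3, state that the primary PFS comparison with 10 months (Cohort A) and 7 months (Cohort B) includes every patient in the cohort who took at least one ceritinib dose, timed from first dose, whether or not SABR was given. Strike the SABR clause as the comparison population.

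The Safety Set already has this membership, so no new set is needed. The Full Analysis Set would not fit exactly: it includes enrolled patients who never took ceritinib, who have no PFS start date and whom section 5.2.3.3 allows to be replaced. The two PFS definitions in section 9.1 must also be reconciled.

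If a SABR-treated result is wanted, label it a secondary landmark analysis from week 10 or SABR start, and do not set it against 10 or 7 months. In simulation, moving the clock to week 10 restores 4.7–5.3% (A) and 4.5–5.1% (B), but only because exponential PFS has no memory. A real benchmark would have to be conditioned on the same 10 weeks, and the documents give none.

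The cost is a wording change in the protocol and SAP. The observed median may be less favourable because early failures count.
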